3.5 Methods for assigning treatment arms

Eligible patients will be randomised by a ratio 1:1:1 to olaparib monotherapy, ceralasertib+olaparib or AZD1775+olaparib combinations. AZD1775+olaparib arm was closed in April 2019 so randomisation ratio will be 1:1 to olaparib monotherapy or ceralasertib+olaparib. The actual treatment given to individual patients will be determined by

a randomisation scheme that has been loaded into the Interactive Voice Response System/Interactive Web Response System (IVRS/IWRS) database.

The process for randomisation and associated Investigator tasks will be outlined in the IxRS manual.

A blocked randomisation list will be generated at PAREXEL Informatics in accordance with AZ Rand. The randomisation scheme will be stratified based on the

- tumour biomarker strata A, B, C defined in Section 1.4
- patient's prior platinum-based therapy (no / yes)

Randomisation in all centres through IxRS will minimise any imbalance in the total number of patients assigned to each treatment arm. The randomisation list will be loaded into the Interactive Response Technology (IRT) system.

Patient eligibility will be established before treatment randomisation. Once the eligibility of a patient has been confirmed, the Investigator (or nominated assistant) should contact the IRT system for allocation of randomised study treatment. The IRT system will inform the Investigator of the Kit identification (ID) number to be allocated to the patient at the randomisation visit. The Investigator will call/log in to the IRT system for each subsequent dispensing visit for assignment of a new Kit ID number. The Kit ID number dispensed at each visit will correspond to the study treatment to which the patient was originally randomised.

It is recommended that patients commence study treatment as soon as possible after randomisation, and ideally within 3 days.

If a patient discontinues participation in the study, then their enrolment/randomisation code cannot be reused.

Once 75 non *HRRm* patients have been recruited, recruitment into this stratum will be paused while the interim futility analysis is conducted. Similarly, if an interim futility analysis is necessary for the non *BRCAm* *HRRm* stratum, recruitment to stratum B will be paused until the analysis is complete.

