8.2 Sample size estimate

In the 3 tumour biomarker strata A, B, C, for each of the 2 comparisons (ceralasertib + olaparib vs olaparib monotherapy, AZD1775 + olaparib vs olaparib monotherapy), 68 PFS events would have 80% power to show a statistically significant difference at the two-sided 10% significance level if the assumed true treatment effects were HR 0.55. This translates to a 5-month benefit in median PFS over 6 months on olaparib in the *BRCAm* stratum and a 4.17-month benefit in median PFS over 5 months on olaparib in the non *BRCAm* *HRRm* stratum and in the non *HRRm* stratum if PFS is exponentially distributed.

Following the decision of the ISRC to close recruitment to the AZD1775 + olaparib arm, the study will only be sized to detect a difference for the ceralasertib + olaparib vs olaparib monotherapy comparison.

Approximately 50 patients (450 patients overall) will be randomised to each of the 3 treatment arms within each of the 3 biomarker strata so that data maturity for the PFS analysis is approximately 68%. Following the closure of the olaparib+AZD1775 arm in April 2019, fewer than 50 patient per strata will be randomised to this arm and the total number of patients randomised will be lower (approximately 350 patients).

Assuming 15 months non linear recruitment, the required number of PFS events are expected to occur approximately 24 months after the first patient is randomised.

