8.5 Methods for statistical analyses

All efficacy analyses will be performed on the FAS. Results of statistical analyses will be presented using 90% CIs and 2-sided p-values.

Pairwise comparisons between the ceralasertib + olaparib vs. olaparib monotherapy, AZD1775+olaparib vs. olaparib monotherapy and ceralasertib + olaparib vs. AZD1775+olaparib will be generated for each endpoint.

Following the decision of the ISRC to close recruitment to the AZD1775 + olaparib arm, the study will only be sized to detect a difference for the ceralasertib + olaparib vs olaparib monotherapy comparison, although all the available data across all 3 arms, where possible, will be used in the statistical models.

As the starting dose of the AZD1775+Olaparib arm was refined during the study, for any comparisons including the AZD1775+olaparib arm, all AZD1775+olaparib patients regardless of their starting dose will be included in the analyses. Additional sensitivity analyses may be carried out which only including those patients AZD1775+Olaparib patients who start treatment on the revised starting dose.

The assignment of a patient to each of the populations will be based on the values entered into IVRS at randomisation, even if it is subsequently discovered that these values were incorrect or not confirmed by the central FMI assay. If there are any patients who were wrongly assigned, a sensitivity analysis may be carried out with patients in the population they should have been assigned to.

The stratification in the statistical modelling will be based on the values entered into IVRS at randomisation, even if it is subsequently discovered that these values were incorrect. If there are any patients who were mis-stratified, a sensitivity analysis will be carried out using the (correct) baseline data collected in the eCRF.

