4.1.8 General principles for statistical modelling and hypothesis testing

All statistical tests will be pairwise, i.e. comparing two treatment arms and there will be no “overall” tests of global null hypotheses (same distribution in all three treatment arms).

Any stratification in the statistical modelling will be based on the values entered into Interactive Voice Recognition System (IVRS) at randomisation, even if it is subsequently discovered that these values were incorrect. In case of at least 10% of mis-stratified patients (across all strata), a sensitivity analysis will be carried out using the (correct) baseline data collected in the eCRF.

Results of statistical analyses will be presented using 2-sided 90% CIs and 2-sided p-values for pairwise comparisons between

- AZD6738+Olaparib versus Olaparib monotherapy
- AZD1775+Olaparib versus Olaparib monotherapy
- and AZD6738+Olaparib versus AZD1775+Olaparib (as secondary analysis).

Two-sided p-values will be presented using 3 decimal places for all values ≥ 0.001 . The only categorical presentation to be used is when $p < 0.001$.

The types of statistical test(s) used to generate p-values or CIs, together with details of any stratification or prognostic factors, should be included in a footnote to the presentation or in

the text as appropriate. Any ‘post-hoc’ analyses (i.e., not pre-specified) will be clearly indicated on any outputs either by using the titles or footnotes as appropriate.

Primary statistical analyses comparing PFS based on BICR for each combination treatment arms to Olaparib will be conducted for the 3 patient populations *BRCAm*, Non *BRCAm* *HRRm* and Non *HRRm*.

Comparisons of PFS based on BICR for each of the combination treatment arms to Olaparib in the 2 patient populations *HRRm* and All will be conducted as secondary statistical analyses.

Secondary outcome measures will be analysed for the 3 patient populations *BRCAm*, Non *BRCAm* *HRRm* and Non *HRRm*, except

- ORR and OS, which will be analysed for all 5 patient populations
- Tumour and germline mutation status, which will be analysed only for the All patient population
- PK outcome measure $C_{\min,ssss}$, which will be analysed only for the All patient population

RECIST-based primary and secondary outcome measures based on Investigator assessments will also be analysed for sensitivity purposes.

Safety outcome measures and exploratory outcome measures will be analysed for the All patient population only, except

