4.2 Analysis Methods

4.2.1 Handling of multiplicity

Multiplicity adjustment will be considered within each of the 3 primary patient populations for PFS. The overall 2-sided alpha for each primary patient population will be 0.2, and a simple Bonferroni adjustment assigns 2-sided alpha of 0.1 to each of the 2 pairwise treatment arm comparisons to Olaparib monotherapy.

No further adjustments for multiplicity are planned, in particular no adjustments for interim analyses.

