4.2.2 Overview of timings of interim and final analyses

For the non *HRRm* population an interim futility analysis will be triggered when 75 patients have been recruited and assessed for at least 8 weeks, in order to assess the proportion of patients with Non Progressive Disease (NPD), based on the Investigator assessment at 8 weeks in each of the treatment arms. Recruitment will be paused after the 75th patient has been recruited into this patient population, until the AZ URC confirms which treatment arms should be reopened. In April 2019, the AZ URC determined that recruitment to the AZD1775+olaparib arm should not be reopened. This parallels the ISRC recommendation to close recruitment to the AZD1775+olaparib arm in all three populations for safety concerns.

A further NPD futility interim analysis in the non *BRCAm* HRR*m* population may be performed, if the outcome of the interim analysis in the non HRR*m* population resulted in treatment arms being stopped.

For each of the 3 primary patient populations (*BRCAm*, non *BRCAm* HRR*m*, non HRR*m*) a further interim analysis for PFS is triggered when 44PFS events for the AZD6738+olaparib vs. olaparib monotherapy pairwise comparison in that particular patient population have occurred. As the non HRR*m* patient population is expected to be enrolled quicker than the other patient populations, it is expected the interim analysis for this patient population will occur first, followed by interim analysis for the 2 other primary patient populations. These PFS interim analyses may be concurrent or separate depending on the recruitment and PFS event rates for the 3 patient populations and other operational requirements.

For each of the 3 primary patient populations (*BRCAm*, non *BRCAm* HRR*m*, non HRR*m*) the final analysis for PFS is triggered when 68 PFS events in that particular patient population have occurred. These final analyses may be concurrent or separate depending on the recruitment and PFS event rates for the 3 patient populations and other operational requirements.

An initial OS analysis will be performed at the same time as the primary analysis of PFS. A further analysis of OS will be performed when the OS data for the AZD6738+olaparib vs. olaparib monotherapy pairwise comparison are approximately 70% mature.

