4.2.3 General time-to-event analysis considerations

Stratification of log rank test and proportional hazards model

Time-to-event endpoints will be analysed using stratified log-rank tests for generation of the p-value and using the Breslow approach for handling ties (Breslow 1974). Hazard ratios and their CIs will be estimated from stratified proportional hazards models (with ties = Efron) and the CIs calculated using a profile likelihood approach. For both approaches, the stratification variables will be included in the STRATA statement of SAS PROC LIFETEST and SAS PROC PHREG, respectively.

Where applicable, stratification factors will be those used in the randomization. It is sensible to have at least 5 events in each stratification cell (combination of the marginal strata). One stratification factor with 2 levels and 3 treatment arms would lead to $2 \times 3 = 6$ stratification cells. Two stratification factors with 2 and 3 levels, respectively, and 3 treatment arms would lead to $2 \times 3 \times 3 = 18$ stratification cells. If the minimum of 5 events in each stratification cell is not reached, then also unstratified analyses will be conducted.

Proportionality assumption

The assumption of proportional hazards will be examined by plots of log-log (event times) versus log (time). If these raise concerns, by fitting a time dependent covariate (adding a treatment-by-time or treatment-by-log(time) interaction term) to assess the extent to which this represents random variation. If a lack of proportionality is evident, the variation in treatment effect can be described by presenting piecewise HR calculated over distinct time-periods (0-16 weeks, 16-32 weeks, 32-48 weeks, etc).

4.2.4 PFS primary analyses based on BICR for patient populations *BRCAm*, *non BRCAm HRRm* and *non HRRm*

The study treatment status at progression of patients at the DCO date used for analysis will be summarised. This will include

- the number (%) of patients who were on study treatment at the time of progression
- the number (%) of patients who discontinued study treatment prior to progression
- the number (%) of patients who have not progressed and were on study treatment
- the number (%) of patients who have not progressed and discontinued study treatment.

Primary analyses of PFS will be based on data from the BICR and conducted separately for the patient populations *BRCAm*, *non BRCAm HRRm* and *non HRRm*, respectively.

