In each of these 3 patient populations, PFS will be analysed using pair-wise log rank tests stratified for prior platinum-based therapy (no, yes) for generation of the p-value. Pairwise HRs and two-sided 90% CIs will be estimated from a proportional hazards model stratified for prior platinum-based therapy (no, yes). The two-sided 80% and 60% CIs will also be estimated.

For each of these 3 patient populations, KM curves for PFS will be presented by treatment arm, overall and separately by prior platinum-based therapy (no/yes).

The number of events, median PFS with two-sided 90% CIs, and the percentage PFS as well as two-sided 90% CIs at 3, 6, 12, 18 and 24 months will be summarised. For calculating these CIs:

- KM estimates will be transformed to an unrestricted range by the $\log(-\log(x))$ function
- calculation of CIs by applying normal approximation methods to the transformed scaled
- re-transformation of CIs to the original scale.

This approach is triggered by option `CONFTYPE=LOGLOG` in SAS PROC LIFETEST.

The progression status at the time of the PFS analysis will also be summarised, including the number and percentage of patients who progressed due to RECIST progression (separately for TLs, NTLs and new lesions) or due to death, or did not progress due to being progression free or due to being lost to follow up or due to withdrawn consent.

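### Comparisons with the closed AZD1775 arm include comparator patients randomised after closure, with no concurrent-control rule or period adjustment

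*Protocol*

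**What the plan says.** Protocol 8.5 performs all efficacy analyses on the FAS, which Protocol 8.3.1 and SAP 2.1.1 define as all randomised patients, with no limit on randomisation date. It keeps all three pairwise comparisons for each endpoint. After noting that the study is now sized only for ceralasertib+olaparib vs olaparib, it adds: "although all the available data across all 3 arms, where possible, will be used in the statistical models".

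SAP 4.1.8 agrees: "Results of statistical analyses will be presented using 2-sided 90% CIs and 2-sided p-values for pairwise comparisons between" all three pairs of arms, both AZD1775 comparisons included. AZD1775+olaparib vs olaparib remains in the primary objective, and SAP 4.2.1 "assigns 2-sided alpha of 0.1 to each of the 2 pairwise treatment arm comparisons to Olaparib monotherapy".

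Allocation changed during the trial. It began as 1:1:1, and Protocol 3.5 then states: "AZD1775+olaparib arm was closed in April 2019 so randomisation ratio will be 1:1" between the two remaining arms.

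The primary test does not account for this change. SAP 4.2.4 says: "In each of these 3 patient populations, PFS will be analysed using pair-wise log rank tests stratified for prior platinum-based therapy". The PFS sensitivity analyses in SAP 4.2.5 address ascertainment, evaluation-time and attrition bias. Those in Protocol 8.5 address AZD1775 starting dose, wrong population assignment and mis-stratification. None uses randomisation date. SAP 2.0 was revised because the arm closed, but it settles only how AZD1775 patients are classified and counted.

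**The concern.** A patient randomised after closure had no chance of receiving AZD1775, so for the two AZD1775 comparisons that patient is not a randomised control. Analysing everyone as randomised does not repair this, because intention to treat protects only groups that were randomised against each other.

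Any change in prognosis between the two periods would appear as a treatment effect. Better prognosis later would make AZD1775+olaparib look worse than olaparib and ceralasertib+olaparib look better than AZD1775+olaparib. Worse prognosis later would reverse both.

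The documents show no such drift, but they do not justify ruling it out. The protocol version that closed the arm also added incurable advanced locoregional disease to inclusion criteria 4 and 5 (labelled a clarification) and retired the AZD1775 cardiac wording in exclusion criterion 9. In stratum C, SAP 4.2.2 plans a gap in time: "Recruitment will be paused after the 75th patient has been recruited into this patient population".

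At stake are the AZD1775 estimates for PFS, ORR, DoR, tumour size change and OS.

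**Working it through.** **The plan's own figure.** Protocol 8.2 gives 68 events for 80% power at HR 0.55, two-sided 10%. Schoenfeld: 4 × (1.645 + 0.842)² / (ln 0.55)² = 69.2, so 70 events. Power at 68 events is 79.4%. The stated figure is reproduced.

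**Non-concurrent share.** The documents give no counts at closure. Inputs are about 350 patients in total (Protocol 8.2) and about 50 per arm per stratum, so 150 in each open arm. In stratum C, a pause at 75 patients under 1:1:1 gives about 25 per arm, and the AZD1775 arm was not reopened (SAP 5.2). Under 1:1:1, concurrent comparators equal AZD1775 patients in number.

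- AZD1775 arm: 350 − 300 = 50.
- Overall: 1 − 50/150 = 67% (53% at a total of 370, 80% at 330).
- Stratum C: 1 − 25/50 = 50%.
- Stratum A or B, remainder split evenly: (50 − 25)/2 = 12.5, and 1 − 12.5/50 = 75% (55% at 370, 95% at 330).

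**Effect of drift.** Within-stratum log-rank tests were simulated with true HR 1, two-sided 10% and exponential PFS. Medians were the plan's olaparib values: 5 months in B and C, 6 in A. Accrual before closure ran over 15 months, with 6,000-10,000 runs per scenario. Group sizes (AZD1775 / concurrent / later) were 25/25/25 in C, 12/12/38 in B and 13/13/37 in A. The drift sizes are assumptions.

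| Later vs earlier hazard | Data cut | C | B | A |
|---|---|---|---|---|
| 0.8 | 24 months | 11.9% | 13.5% | 13.6% |
| 0.8 | 30 months | 13.5% | 15.7% | 15.9% |
| 0.8 | complete follow-up (5-month median) | 14.3% | 16.8-17.0% | 16.8-17.0% |
| 0.7 | 24 months | 14.2% | 18.2% | 17.1% |
| 0.7 | 30 months | 16.5% | 21.2% | 20.6% |
| 0.7 | complete follow-up (5-month median) | 20.7% | 24.5-24.7% | 24.5-24.7% |

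Median HR, AZD1775+olaparib vs olaparib, at the 30-month cut:

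- 0.8: C 1.11, B 1.18, A 1.17.
- 0.7: C 1.17, B 1.30, A 1.27.

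With no drift, rejection is 10.4-11.2%. Concurrent-only under drift gives 10.6-12.0% with HR 0.99-1.01.

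**Second simulation, both directions.** This used 10,000 runs, 6 months of accrual after closure and a data cut 3 months after that. For 25/25/25, a later hazard of ×0.8 gives HR 1.08 and 12.2%; ×1.25 gives HR 0.92 and 11.8%. For an average stratum of 17/17/33, ×0.8 gives HR 1.12 and 13.5%; ×1.25 gives HR 0.90 and 11.4%. At ×1.25, rejections favouring AZD1775 are 11.8 − 2.9 = 8.9% and 11.4 − 2.6 = 8.8%, against a nominal 5%.

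**Price of restricting.** Ratio of CI widths on the log scale, concurrent-only to all patients:

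- C: √[(2/25) / (1/25 + 1/50)] = 1.15
- A or B: √[(2/12.5) / (1/12.5 + 1/50)] = 1.26
- Pooled: √[(2/50) / (1/50 + 1/150)] = 1.22

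**The case against.** The strongest reply is that little depends on these comparisons. The arm closed for toxicity and no suggestion of benefit, the drug is no longer supplied, and sizing has moved to ceralasertib+olaparib vs olaparib. The alpha of 0.1 for AZD1775 is largely inherited wording. This stands, and it limits the weight of the point.

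The sentence about using all available data can also be read as meaning only that closed-arm data are kept. That is fair, but the FAS rule alone leads to the same analysis.

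The magnitudes rest on assumed drift and inferred counts, and at a total of 330 strata A and B would have about 2.5 AZD1775 patients each, too few for any test. This also stands. In C with 20% drift, the gain from restricting is only about 1 to 3 percentage points.

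There is a bias-variance argument as well. At 20% drift the all-patient log HR has the smaller root mean square error: 0.29-0.30 vs 0.30-0.31 in C and 0.40-0.42 vs 0.47-0.48 in B. At 30% the two are about equal (0.32 vs 0.31 in C, 0.46 vs 0.47 in B). On that view the FAS could stay as the main analysis, with concurrent-only as sensitivity. But the advantage depends on drift being small, which is unknown, and it does not make patients who were never co-randomised a randomised control.

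Finally, two AZD1775 starting doses are pooled and patients could continue on olaparib 300 mg after closure. The comparison stays hard to interpret under either rule.

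**Conclusion.** The concern holds. Both documents keep p-values and 90% CIs for the AZD1775 comparisons on all randomised patients, and neither contains a concurrent-control rule, a period term or a period sensitivity analysis. The defect is the lack of protection, not a demonstrated bias.

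For a 20% lower later hazard, type I error is about 13% in C (12-14%) and 16% in A or B (14-17%). For 30% it is about 17% (14-21%) and 21% (17-25%). These figures rest on about 350 patients in total, 150 per open arm, the even A/B split, the accrual pattern and the drift itself. With no drift both analyses are valid.

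The point should be corrected because the remedy is cheap, but it does not threaten the trial's main conclusion: ceralasertib+olaparib vs olaparib stayed 1:1 throughout.

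**What to change.** State in SAP 4.1.8 that every comparison involving AZD1775+olaparib, for every endpoint, uses only patients randomised in the same stratum while that arm was open to randomisation. Define the window by stratum, because the stratum C pause may have ended AZD1775 allocation there on a different date. Keep the all-patient analysis as a labelled sensitivity analysis, and align the sentence in Protocol 8.5. Leave ceralasertib+olaparib vs olaparib on the full FAS.

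The work is SAP wording and a randomisation-date filter. The statistical cost is AZD1775 CIs wider by about 15% in C, 26% in A and B, and 22% pooled, on a comparison the study is no longer sized for. In A and B the concurrent set is about 12 vs 12. Split evenly by prior platinum at 68% maturity, that is 6 × 0.68, or about 4 events per cell, so the existing rule in SAP 4.2.3 would apply: "If the minimum of 5 events in each stratification cell is not reached, then also unstratified analyses will be conducted".

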8.5.1 Analysis of the primary variable (s)

Primary analysis of PFS will be based on data from the BICR; sensitivity analyses of PFS are described further below.

Patient populations: *BRCAm, non BRCAm HRRm, non HRRm* (primary analysis)

In each of these patient populations, PFS will be analysed using pair-wise log rank tests (using the Breslow approach for handling ties) stratified by prior platinum-based therapy for generation of the p-value.

The pairwise HRs and confidence intervals will be estimated from a stratified Cox Proportional Hazards model (with ties = Efron) with a prior platinum-based therapy (Y/N) term included in the strata statement and the CIs calculated using a profile likelihood approach.

For each patient population, a KM plot of PFS will be presented by treatment group (overall and stratified by prior platinum-based therapy).

Patient population: HRR_m (secondary analysis)

To achieve an estimated pairwise HRs for PFS that are representative of the HRR_m patient population, the following approach will be implemented:

1. PFS will be analysed using pair-wise log rank tests (using the Breslow approach for handling ties) stratified by prior platinum-based therapy separately in stratum A and stratum B
2. pair-wise HRs (separately for stratum A and stratum B) will be obtained directly from the Cox Proportional Hazard Model
3. a weighted estimate of the HR_{HRR_m} will be calculated using the estimated HR in stratum A (HR_A) and the estimated HR in stratum B (HR_B):

$$\ln(HR_{HRR_m}) = w_1 \ln(HR_A) + w_2 \ln(HR_B)$$

where weights w_1 and w_2 will be estimated from external literature and the study's screening records

4. For calculation of CIs, the overall variance (log scale) will take into account the variance of both groups (that are independent), and thus be calculated as:

$$\text{var}(\ln(HR_{HRR_m})) = w_1^2 \text{var}(\ln(HR_A)) + w_2^2 \text{var}(\ln(HR_B))$$

As a sensitivity analysis, PFS will be analysed using an unweighted log rank test stratified by biomarker status (stratum A, stratum B) and prior platinum-based therapy for generation of the p-value and using the Breslow approach for handling ties.

The pairwise HRs and confidence intervals will be estimated from a stratified Cox Proportional Hazards model (with ties = Efron) with biomarker status (stratum A, stratum B) and a prior platinum-based therapy (Y/N) term included in the strata statement and the CIs calculated using a profile likelihood approach.

KM plots of PFS will be presented by treatment group (overall and stratified by prior platinum-based therapy).

Patient population: All (secondary analysis)

Similar weighted and unweighted analyses as described above will be conducted for the All patient population; now with 3 weights to combine the HR estimates and its variances for the 3 strata A, B and C.

Sensitivity analyses for the 3 primary analyses of PFS

(a) Ascertainment bias

The possibility of bias in assessment and measurement of PFS by BICR will be assessed by comparing the HRs derived from BICR with the HR derived using the Investigators’ review assessment of disease progression by RECIST.

(b) Evaluation-time bias

In order to assess possible evaluation-time bias, that could occur if scans are not performed at the protocol-scheduled time points, the midpoint between the time of progression and the previous evaluable RECIST assessment will be analysed using a stratified log rank test, as described for the primary analysis of PFS. For patients who die in the absence of progression, the date of death will be used to derive the PFS time used in the analysis.

(c) Attrition bias

Possible attrition bias will be assessed by repeating the primary PFS analysis, except that the actual PFS event times, rather than the censored times, of patients who progressed or died in the absence of progression immediately following two, or more, non evaluable tumour assessments will be included. In addition, patients who take subsequent therapy prior to progression or death will be censored at their last evaluable assessment prior to taking the subsequent therapy. A KM plot of the time to censoring, where the censoring indicator of the primary PFS analysis is reversed, will be presented.

